- 2 * Discuss the research design including but not limited to such issues as: probability of group assignment, potential for subject to be randomized to placebo group, use of control subjects, etc.:

Volunteers with a DSM-IV diagnosis of schizophrenia or schizoaffective disorder will be recruited, screened, and allocated in a double-blind manner to either the Nicotine Group or the Placebo Group. All participants will be asked to perform 10 weeks of cognitive remediation training (Posit Science, Duncan, SC), with daily training sessions Monday through Friday. On Mondays and Thursdays, all participants receive a lozenge 20 min prior to the training. In the Nicotine Group, the lozenge will contain 2 or 4 mg of nicotine, depending on smoking status. In the Placebo Group, the lozenge will be a matched placebo.

Outcome measures (OCMs) are assessed on Wednesdays in week 0 (day before training starts), weeks 4, 7 and 10 (after the training session), and week 14 (four weeks after training ends). OCMs are assessed on a non-drug day (Wed) because we are not studying the acute effects of nicotine but nicotine-induced enhancement of longer-term training effects.

- 3 * Describe the relevant prior experience and gaps in current knowledge. Describe any relevant preliminary data:

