Volunteers who provide Informed Consent will be screened for all Inclusion/Exclusion criteria. SCREENING will include: - Verification of age. - The SCID, to determine the presence/absence of current psychiatric conditions. For most patients, a SCID will have already been obtained and does not need to be repeated. - Medical history targeted at the cardiovascular, neurological, cognitive and other exclusion criteria. - Blood pressure and heart-rate reading. - ECG (12-lead with 3-5 minute rhythm strip). Exclusionary conditions documented on ECG include: Wolfe Parkinson White syndrome Myocardial ischemia and infarction Complete left bundle branch block PR interval <120 ms or >200 ms Prolonged QT interval (corrected) >500 ms Cardiac arrhythmias as defined by PACs >3 per min or PVCs >1 per min - Urine drug test, as a possible indication for substance abuse or dependence (may be repeated at any time during the study if intoxication is suspected) - Alcohol breathalyzer test, as a possible indication for alcohol abuse or dependence (may be repeated at any time during the study if intoxication is suspected) - Urine pregnancy test for females (also performed at the beginning of the cognitive training phase, and every two weeks thereafter) - Targeted questions about smoking history and motivation to stop smoking - Breath CO reading, as an indicator of smoking status and frequency - Listing of all currently taken medication - Vision test - The Addiction Severity Index - Drug and Alcohol Use subscale as an indicator for substance abuse or dependence. - The Wechsler Abbreviated Scale of Intelligence (WASI), as an indicator for possible mental retardation. Volunteers who pass the screening will be randomized to either the nicotine group or the placebo group. Randomization will be performed by the MPRC's biostatistician, [name], upon receiving a randomization request from the research assistant coordinating the study or a study investigator. Participants are then scheduled for a first NICOTINE EXPOSURE SESSION. In this session, participants will consume a nicotine lozenge (2 mg for non-smokers, 4 mg for smokers) if they have been randomized to the nicotine group and a placebo lozenge if they have been randomized to the placebo group. The number of smokers will be counterbalanced between the nicotine and placebo group. Participants will be instructed not to eat or drink within 15 min prior to or while consuming the lozenge. Participants are asked to report any adverse effects as soon as noted and to rate their subjective state immediately before the lozenge and every 30 min thereafter (see Side-Effects Checklist under "Additional Documents"). At this time, an investigator will also take their blood pressure and heart rate. The adverse effects of nicotine develop rapid tolerance. If any adverse effects are observed that are greater than "mild" and were not present pre-lozenge, the participant will undergo another lozenge exposure session on a separate day before starting the study. This may be repeated up to 4 times. Once both the participant and the investigator judge that any untoward effects of the lozenge are mild and tolerable and will not interfere with the cognitive training, the first outcome measurement session is scheduled, and the daily training sessions will commence the day after. A smoker who cannot tolerate the 4-mg lozenge may be dosed with a 2-mg lozenge in the cognitive training phase (the study would be single-blind for this subject). A participant who cannot tolerate the 2-mg lozenge even after repeated attempts will be excluded from the study. Participants who with the 2 mg lozenge display a rise in blood pressure by >20 mm Hg relative to pre-lozenge, a rise in HR to >120, or vomiting, will also be excluded from the study. OUTCOME MEASUREMENTS will be performed before the training begins, and approximately every 4 weeks after that until 4 weeks after the training ends. During the training phase, the outcome measurements will be performed AFTER completion of the daily cognitive training session. We will always schedule at least 1 hour between training and the outcome measurement, during which the participant can rest or have lunch. Outcome assessments are: a) The MATRICS Consensus Cognitive Battery (MCCB), an FDA-approved assessment tool for trials of cognition-enhancing treatments in PSZ. The battery measures 7 domains: speed of processing, attention/vigilance, working memory (verbal, nonverbal), verbal learning, reasoning, problem solving, and social cognition. b) The progression in training exercise parameters since the last outcome measurement time point (see below). c) Symptom assessments: the Brief Psychiatric Rating Scale, Scale for Assessment of Negative Symptoms, and Calgary Depression Scale. d) The state version of the State-Trait Anxiety Inventory. e) The Cogstate computerized assessment battery. Further outcome measures taken only pre- and post-training (week 0 and 10): a) Working Memory capacity (K) derived from a computerized change localization task. Two to four colored squares are shown for 100 ms. After a delay, they reappear and the task is to click on the one square that has changed color. b) The UCSD Performance-Based Skills Assessment, measuring ability to perform real-life tasks by standardized role-play. c) Quality of Life Scale, measuring functional outcome and quality of life in PSZ. d) The trait version of the State-Trait Anxiety Inventory. e) The Cognitive Assessment Interview (CAI), a brief interview-based measure of daily life cognitive functioning, administered to both the PSZ and a close relative or caretaker. The CAI was developed based on two longer scales and assesses 10 items related to working memory, attention/vigilance, learning/memory, problem solving, processing speed, and social cognition, with little or no repetition effects. f) Questionnaire asking each participant to guess their treatment group (nicotine or placebo; post-training only). g) A 5-ml venous blood sample will be taken, centrifuged, and frozen. At the completion of the study, the samples will be analyzed for TNF alpha, and potentially other inflammatory markers, to test whether repeated nicotine exposure may have anti-inflammatory effects that may be related to any effects on cognitive outcome measures. If a participant declines to have their blood drawn but are otherwise eligible for the study, they may participate without the blood draws. COGNITIVE REMEDIATION TRAINING PROCEDURE Prior to each daily training session, participants will complete a brief checklist about their caffeine and cigarette consumption today (how much/how many), when they last smoked/drank a caffeinated beverage, how many hours of sleep they got the previous night, when they last drank alcohol and how much. Prior to each session, smokers also provide a CO breathalyzer reading. Each training session will include ~30 min of auditory and ~30 min of visual training exercises by Posit Science, in a counterbalanced manner. The auditory training consists of six exercises: fast and accurate discrimination of (1) sound frequencies, (2) phonemes and (3) syllables, and recall of syllables, (4) sequences of syllables, (5) multi-element verbal instructions, and (6) details of a narrative. The visual training consists of five exercises designed to (1) improve visual precision, (2) increase capacity to divide visual attention, (3) improve visual memory, (4) expand field of view, and (5) increase visual processing speed. The programs train the fine-tuned and differentiated processing of sensory input and engage attention, working memory and/or executive processes. To induce the right level of challenge and promote engagement and motivation, task difficulty adjusts continuously to user performance to maintain ~85% correct responses (which are rewarded by auditory and visual feedback). Adjustable parameters include presentation time, interstimulus interval, physical similarity between stimuli, stimulus eccentricity, number of stimuli, and information complexity. Some exercises provide a progress summary of these parameters after each session. These values will be recorded on all training days. Other exercises provide a separate assessment tool to monitor progress. These assessments will be performed every 4 weeks with other outcome measurements. Every Monday and Thursday, a nicotine or placebo lozenge, encapsulated in gelatin, will be administered 20 minutes prior to the beginning of the training. Nicotine lozenges are mint-flavored "mini" lozenges, placebo lozenges are size-matched breath mints. Smokers in the Nicotine Group will receive a 4-mg lozenge. Plasma concentrations after this dose resemble the "nicotine boost" typically seen in dependent smokers by smoking a single cigarette (~1 ng/ml). Non-smokers in the Nicotine Group will receive a 2-mg lozenge because 4 mg in nicotine-naïve individuals would likely result in low tolerability. Participants will be instructed not to eat or drink within 15 min prior to or while consuming their lozenge. Participants may perform the training sessions at the Maryland Psychiatric Research Center (MPRC), or, in a separate room, at their day program or inpatient unit if applicable (a research associate would visit daily with laptop, lozenge or assessment instruments). The lozenge would be administered by a local nurse or other medical professional if possible, else these sessions would be performed at the MPRC. Participants who are unable to come to the MPRC or day program to complete the training (e.g., because they work or live too far away) may perform the exercises at home if they have internet access and their clinician or study staff considers them capable of doing so reliably. The CO measurement would be omitted on home-training days, and participants would be given the questionnaire about how much they slept and how much caffeine or alcohol they consumed to complete by themselves at home. On the two weekly lozenge days, they would be scheduled to perform the training at the MPRC. Under select circumstances, when the patient is unable to come to the MPRC on those days, too, they would be instructed to take the lozenge at home, following doctor's orders. A study team member would call them at home and

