If you uploaded a separate research protocol document in the 'Research Protocol' page, cite the applicable section and page numbers from that document in the answer boxes below.

- 1 * Provide the rationale and sample size calculations for the proposed target population:

Statistical and power analyses: Hypothesis 1a (larger or faster improvement in Nicotine than Placebo Group): Assuming training effects are linear with time, we will conduct an intention to treat (ITT) analysis by fitting the mixed model regression for repeated measures OCM= time+ treatment+ treatment x time, with time as a continuous measure. The treatment x time interaction estimates the difference between treatment groups in OCM rate of change (slope). Although we will include subjects with partial data, the effect size detectable was estimated conservatively⁷⁸ by: $d = [2(z_a + z_b)2(1-r)/bnVar(t)]/2$, where d = (difference in slopes)/SD(OCM), r = within-subject correlation of OCM, $b=4$ visits per subject, n = number of completers per group, $Var(t)=0.185$ is the within-subject variance of the visit times, and $z_a=1.96$ and $z_b=0.84$ for two-sided $\alpha=0.05$ and power=0.80. With $n=20$ completers per group, $d=0.56$ (a medium effect size) will be detectable for $r=0.7$ consistent with the high ICC of the MCCB, the primary OCM. To explore differences in treatment effects between MCCB domains, we will employ the mixed model for repeated measures: T-score= domain+ treatment+ time+ interactions. In particular, the domain x treatment x time interaction assesses variation among domains in the magnitude of the treatment effects on change slopes in OCM scores. In secondary analyses to guide the design of future studies, we will fit a model in which time is treated as a categorical measure unconstrained by a linear fit to explore different learning scenarios such as a more rapid initial acquisition but similar ceiling. In this model, we will add week 14 data to examine Hypothesis 1b (persistence of improvements after training ends), comparing treatment groups on the difference between week 14 and 10. Other exploratory analyses: 1) Smoking status (smoker, never-smoker) is added as an exploratory between-subject factor. 2) A further regression will explore differences between treatment groups in two compliance measures, the cumulative percentage of missed training sessions and lozenge administrations until each OCM time point. If treatment groups differ on compliance, we would include time-dependent compliance as a mediator of treatment effects. A descriptive analysis to support Hypothesis 1a will compare the percentage of participants in each group that achieves clinically significant improvement in MCCB composite scores (6 points from baseline adjusted for practice effects, see above) at each OCM time point.

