- Due to potential overlap of smoking-derived and lozenge-derived blood nicotine, some smokers may be exposed to more nicotine than they are used to. However, the slow rise of lozenge-derived blood nicotine will coincide with the metabolism of cigarette-derived nicotine, even if a cigarette was smoked immediately before the session. Thus, side effects due to this scenario are expected to be mild and rare. Risk minimization: Participants are asked not to chew the lozenge or swallow it whole. The lozenges dissolve over 10 min, thus enforcing a relatively slow rise in nicotine blood levels.

- Nicotine may be harmful to a born or unborn baby. It is secreted in breast milk and crosses the placenta. If nicotine was given to a pregnant or lactating female, this risk would be likely and relatively serious. Risk minimization: Pregnant or lactating females are excluded from study participation.

b) Participants may find the cognitive training exercises boring or tiring. This is a likely but non-serious risk.

Risk minimization: The exercises adjust their difficulty to maintain participants' performance at 85%, provide positive reinforcement for correct responses, and are perceptually engaging. Participants may take breaks.

c) Cognitive testing: Participants may find the MATRICS Battery, Change localization task, Posit Science evaluation programs, and other outcome assessments boring, difficult or frustrating. This is a relatively likely but minor risk.

Risk Minimization: Participant may take breaks as needed. If all assessments cannot be performed in one session, they may be completed on a separate day (usually after training on the following Friday, i.e. the next no-lozenge day). Furthermore, many assessments stop when a difficulty level is reached at which the participant's performance brakes off. The testers have extensive clinical experience, conduct assessment sessions in a highly supportive fashion and are accustomed to working with patients in more demanding protocols than the current one.

d) Questionnaires and Characterization Measures: Some of the questions asked may be perceived as embarrassing. This is a relatively likely but minor risk.

Risk Minimization: The confidentiality of all replies will be ensured and emphasized to participants. Participants will be advised during consenting that they may refuse to answer any questions that cause them discomfort.

e) Loss of confidentiality or privacy. This is a serious but unlikely risk.

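### Placebo-group smokers may train with cigarette nicotine on board, yet the Hypothesis 2a/2b analyses carry no smoking factor, and no CO or last-cigarette reading is scheduled at weeks 0 and 14

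*Combined protocol and SAP*

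**What the plan says.** **Who is enrolled.** Eligibility admits people who currently smoke and are not attempting to quit, and people with almost no lifetime smoking. Study Procedures (item 1) counterbalances the number of smokers between groups. In the Nicotine Group, smokers receive 4 mg and non-smokers 2 mg. A smoker who cannot tolerate 4 mg may be given 2 mg.

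**Smoking around sessions.** The stated restriction before a lozenge concerns food and drink. Research Related Risks, part a), says that the lozenge rise will coincide with the metabolism of cigarette nicotine "even if a cigarette was smoked immediately before the session". Study Procedures compares plasma levels after the 4-mg lozenge with the boost "typically seen in dependent smokers by smoking a single cigarette".

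**What is recorded.** A checklist before each daily training session asks about cigarettes that day and when the participant last smoked. "Prior to each session, smokers also provide a CO breathalyzer reading". CO is omitted on home-training days, and the questionnaire for home use is described only in terms of sleep, caffeine and alcohol. Surveys/Questionnaires assigns the checklist to training days.

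**What is analysed.** In Sample Size and Data Analysis (item 1), smoker versus never-smoker is an exploratory factor listed with the Hypothesis 1a and 1b analyses. Hypothesis 2a is a t-test between groups on within-session progress averaged over 20 lozenge sessions. Hypothesis 2b looks at progress in no-lozenge sessions (Tuesday, Friday) and compares it with the same sessions in the placebo group. Neither has a smoking term. CO and time since last cigarette appear in no analysis.

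**When outcomes are tested.** Justification, Objective, & Research Design (item 2) sets tests at weeks 0, 4, 7, 10 and 14, and explains: "OCMs are assessed on a non-drug day (Wed) because we are not studying the acute effects of nicotine".

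**The concern.** Hypothesis 2a is the mechanistic test: does progress within a session improve when nicotine is present? In a never-smoker, lozenge against placebo is nicotine against none. In a smoker it may be lozenge plus recent cigarette against recent cigarette alone, and the protocol itself treats the two sources as similar in size. If that is common, the contrast shrinks. A null result could then mean either that nicotine does not help or that placebo smokers also had nicotine. The planned analysis cannot help to tell these apart, because it does not separate smokers from never-smokers.

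A second, smaller issue concerns the outcome tests. The protocol's background (item 3 of the same design section) says that nicotine enhances these functions acutely and that withdrawal impairs them. Time since the last cigarette can therefore move a smoker's score either way on a test day. Week 0 is the start of every Hypothesis 1a slope and week 14 is the follow-up point for Hypothesis 1b, yet neither has a reading attached.

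**Working it through.** **1. The plan's own figure.** For Hypothesis 2a the inputs are z-values 1.96 and 0.84, b = 20 sessions, n = 20 completers per group and r = 0.3. Reading the formula with a square root and 1 + (b - 1)r:

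d = sqrt[2 × (1.96 + 0.84)² × (1 + 19 × 0.3) / (20 × 20)] = sqrt[15.68 × 6.7 / 400] = 0.512.

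This matches the stated 0.51. The printed minus sign would give a negative quantity under the root and may be a typing or PDF-reading error.

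**2. Coverage of the readings.**

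| Occasion | CO and last-cigarette reading | Used in an analysis |
|---|---|---|
| Training sessions on site | Yes, before training | No |
| Home-training days | CO no; home questionnaire described without smoking | No |
| Tests at weeks 4, 7, 10 | Only the reading from before that day's training | No |
| Tests at weeks 0 and 14 | None scheduled | - |

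At weeks 4, 7 and 10 the test follows the session (about 60 minutes of exercises in Study Procedures, 80 minutes in Behavioral Intervention) and a break of at least 60 minutes. The reading is thus at least about 120 to 140 minutes old, with no smoking restriction stated for the break. The CO reading at screening indicates smoking status and frequency; it is not tied to the week-0 test.

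**3. Dilution, as an illustration only.** The documents give neither the share of smokers (s) nor the share of their sessions preceded by a recent cigarette (p), nor how much of the lozenge effect survives a recent cigarette (k). All three are assumed here.

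Retained effect = 1 - s × p × (1 - k). Power = Φ(2.8 × retained - 1.96), for a test with 80% power against the undiluted effect.

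| s, p | k = 0: retained, power | k = 0.5: retained, power |
|---|---|---|
| 0.4, 0.3 | 0.88, 69% | 0.94, 75% |
| 0.5, 0.5 | 0.75, 56% | 0.875, 69% |
| 0.6, 0.8 | 0.52, 31% | 0.76, 57% |

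For the middle row: k = 0 gives Φ(2.8 × 0.75 - 1.96) = Φ(0.14) = 0.56, and k = 0.5 gives Φ(2.8 × 0.875 - 1.96) = Φ(0.49) = 0.69. With k = 1 there is no loss.

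**4. What a stratum estimate can show.** With s = 0.5 there are about 10 completers per group in each stratum. The detectable effect is then sqrt[15.68 × 6.7 / (20 × 10)] = 0.72, against 0.51 overall. For a difference between the two strata it is 0.72 × sqrt(2) = 1.02. The interaction is therefore descriptive at this sample size.

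**The case against.** The strongest reply is that adding a lozenge to usual smoking is a legitimate randomised contrast. Smokers are counterbalanced, so cigarettes on board add noise and dilution but not bias between groups. That stands. A reader might infer that the trial's comparison is invalid; the documents do not support it.

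Second, the sentence about a cigarette just before a session comes from a safety paragraph. That paragraph says some smokers may get more nicotine than they are used to, and describes the lozenge level rising while cigarette nicotine is metabolised. The same section puts the lozenge peak at about one hour. Training starts 20 minutes after the lozenge, so the peak falls about 40 minutes into the session. A lozenge that adds nothing after a cigarette is thus a worst case, and the k = 0 column should not be read as an expected loss.

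Third, that smokers may smoke up to the tests is an inference from the absence of a rule; no section says so. Testing on a non-drug day can be read as a day without the study lozenge, which the plan achieves. Since withdrawal is said to impair the same functions, testing under usual smoking is not plainly a flaw.

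Fourth, Hypothesis 2b might be taken for another comparison of nicotine present against absent. It is not: it compares no-lozenge sessions between groups, to see whether earlier gains carry over.

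Fifth, never-smokers may look like an uncontaminated estimate of the nicotine effect. They receive 2 mg and smokers 4 mg, so a difference between strata mixes smoking with dose.

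What none of this answers is that a factor the trial balances and doses by is left out of its mechanistic analyses, and that readings already collected have no stated use.

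**Conclusion.** The point holds in a limited form. Placebo-group smokers may train with nicotine that the protocol likens to the active 4-mg dose. The size of the resulting dilution of Hypothesis 2a is unknown and cannot be derived from the documents. Over the assumed ranges (smokers 40-60% of the sample, a recent cigarette before 30-80% of their sessions), 76-94% of the effect remains if the lozenge keeps half its effect after a cigarette, and 52-88% if it keeps none. These figures illustrate why a null result would be hard to read; they are not a forecast of power.

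The gap in the plan is definite: no smoking factor in the Hypothesis 2a/2b analyses, no use of CO or time since last cigarette, and no reading scheduled at weeks 0 and 14. It is a minor weakness of interpretation. The primary intention-to-treat analysis of Hypothesis 1a needs no change.

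**What to change.** 1. **Hypothesis 2a.** Replace the t-test on per-participant averages with a linear model on the same averages containing group, smoking status and their interaction. Report the overall group effect and the estimate in each smoking stratum with confidence intervals. State that stratum is confounded with dose (2 against 4 mg), that a smoker moved to 2 mg is an exception, and that each stratum is imprecise.
2. **Hypothesis 2b.** Use the same model for per-participant progress in the no-lozenge sessions.
3. **Readings.** Take the existing CO reading (smokers) and last-cigarette question immediately before testing at every outcome visit: weeks 0, 4, 7, 10 and 14.
4. **Use of the readings.** Pre-specify them as covariates in labelled sensitivity analyses only: Hypothesis 1a on weeks 0-10, and Hypothesis 1b with week 14 in the categorical-time model. State how never-smokers, who give no CO reading, are coded. Smoking during the trial is post-randomisation, so these analyses must not replace the randomised comparison.
5. **Training-day readings.** Tabulate time since last cigarette and CO before lozenge sessions by group, noting that home-training days are incomplete. This needs no model and shows how common recent smoking was.

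The cost is revised analysis wording and a few minutes at each of five visits, with equipment and a form already in use. The changes aid interpretation; they do not restore any lost power. Whether smoking before sessions should be restricted is for the investigators and is not proposed here.

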3 *** Describe how the potential risks to participants are reasonable in relationship to the potential benefits:**

The risks related to administration of nicotine, cognitive training and testing, questionnaire and interview administration, handling of private information, and blood draws will be minimized as outlined above. We consider these risks to be very low in comparison with the scientific and clinical merits to be gained, which may contribute to finding a treatment intervention that can alleviate some of the most debilitating symptoms of schizophrenia.

4 *** Describe the alternatives to participation in this study. If there are no alternatives, state that participation is voluntary and the alternative is not to participate. For intervention studies, describe appropriate alternative clinical procedures or courses of treatment available to subjects.**

Participation is voluntary, and the alternative is not to participate. There are currently no FDA-approved treatments for the cognitive deficits seen in schizophrenia.

ID: VIEW4E1B5251B0400

Name: v2_Potential Benefits and Alternatives

View: v2_Withdrawal of Participants

Withdrawal of Participants

If the questions below are not applicable to the research (i.e., chart review), enter "N/A".

1 *** Describe anticipated circumstances under which subjects will be withdrawn from the research without their agreement:**

Participants may be withdrawn if they display adverse effects of nicotine that would make their continued participation in the study unsafe (see "Study Procedures" for stop criteria), if they cannot or do not follow instructions (for example, will not engage in any of the cognitive exercises despite the individually adjusted difficulty levels), or if a participant is missing too many study days (see "Study Procedures" for criteria of study exclusion).

2 *** Describe procedures for orderly termination:**

Participants are informed that their study participation is terminated, and they are paid for their time up to this time point.

3 *** Describe procedures that will be followed when subjects withdraw from the research, including partial withdrawal from procedures with continued data collection:**

Withdrawal would end any procedures associated with the study. If participants withdraw or are withdrawn due to nicotine side effects, they will be asked to stay on at the MPRC for continued monitoring until symptoms have subsided and the study physician considers it safe for them to leave.

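### Outcome testing ends at withdrawal, so the primary slope comparison targets the effect had everyone continued training, not the stated intention-to-treat effect

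*Combined protocol and SAP*

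**What the plan says.** **Withdrawal of Participants, item 1** lists when staff may withdraw someone without agreement. Besides unsafe adverse effects of nicotine, the grounds are "if they cannot or do not follow instructions (for example, will not engage in any of the cognitive exercises" and so on, and "if a participant is missing too many study days". For the missed-day criterion it refers the reader to Study Procedures.

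**Withdrawal of Participants, item 3** is a form question that asks for the procedures on withdrawal, "including partial withdrawal from procedures with continued data collection". The answer is "Withdrawal would end any procedures associated with the study". The one exception is safety monitoring on site until nicotine side effects subside. No status is described in which a participant has stopped lozenge or training but is still assessed.

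**Sample Size and Data Analysis, item 1** says of Hypothesis 1a: "we will conduct an intention to treat (ITT) analysis by fitting the mixed model regression for repeated measures", with time continuous and linear. On incomplete data it says only "Although we will include subjects with partial data, the effect size detectable was estimated", followed by the power formula. It gives no missing-data assumption and no sensitivity analysis. The same section plans 25 entering training and 20 completing per group.

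**Study Procedures, item 1** schedules several measures only at weeks 0 and 10: working-memory capacity, the UCSD skills assessment, the Quality of Life Scale, trait anxiety, the Cognitive Assessment Interview and the blood sample.

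**The concern.** An intention-to-treat comparison needs outcomes from people as randomized, whether or not they stayed on training. Here the rule that ends someone's participation also ends their outcome data. Part of the missingness is therefore built into the protocol and does not come from refusal.

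Including partial data does not repair this. A person withdrawn after week 4 contributes weeks 0 and 4, and the model treats the unseen weeks 7 and 10 as if training had gone on. Gains from training cannot be expected to keep accruing once training stops.

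The week-0 and week-10 measures are worse placed, because with two time points a person withdrawn in between has no change score. The week-14 versus week-10 comparison for Hypothesis 1b loses the same people.

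The missed-day threshold adds to the problem. Study Procedures contains no such criterion, so an unwritten judgement decides whose outcomes stop.

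**Working it through.** **Inputs.** Visits at weeks 0, 4, 7 and 10 (Justification, Objective, & Research Design, item 2). From Sample Size and Data Analysis, item 1: r = 0.7, b = 4, n = 20 completers per group, Var(t) = 0.185, z-values 1.96 and 0.84, and 25 entering to give 20 completing. The share, timing and arm split of withdrawals are not given, so they are assumptions below.

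**1. The plan's own figure.** d = √[2(z_a+z_b)²(1−r)/(b·n·Var(t))] = √[2 × 2.80² × 0.3/(4 × 20 × 0.185)] = √(4.704/14.8) = 0.564, which matches the stated 0.56. Non-completion is 1 − 20/25 = 20%. The implied standard error is 0.564/2.80 ≈ 0.20.

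**2. What the planned data give.** Suppose those who withdraw had the same on-training slope as the rest of their arm. Every score they contribute then lies, on average, on the on-training line. A linear mixed model fitted to those scores returns the on-training slope, whatever happens afterwards.

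**3. What four visits from everyone would give.** The mean of 0, 4, 7, 10 is 5.25. The deviations are −5.25, −1.25, 1.75 and 4.75, with sum of squares 54.75. Take an on-training gain of 1 unit per week that plateaus when training stops. The fitted slope is Σ(deviation × score)/54.75:

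| Stops | Scores at 0, 4, 7, 10 | Fitted slope | Arm slope with 20% stopping | Planned ÷ ITT |
|---|---|---|---|---|
| right after week 0 | 0, 0, 0, 0 | 0 | 0.8 + 0.2 × 0 = 0.800 | 1.25 |
| week 4 | 0, 4, 4, 4 | 21/54.75 = 0.384 | 0.8 + 0.2 × 0.384 = 0.877 | 1.14 |
| week 7 | 0, 4, 7, 7 | 40.5/54.75 = 0.740 | 0.8 + 0.2 × 0.740 = 0.948 | 1.05 |

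With equal stopping in both arms, the slope difference shrinks by the same factor as each arm's slope.

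**4. Other shares, week-4 plateau.** With 10% stopping: 0.9 + 0.1 × 0.384 = 0.938, ratio 1.07. With 30%: 0.7 + 0.3 × 0.384 = 0.815, ratio 1.23.

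**5. On the plan's scale.** With 20% stopping at week 4, 0.56 × 0.877 = 0.49. The shift of 0.07 is about a third of the standard error of 0.20. By the plan's formula, 25 per group at 0.49 has power of about 0.78.

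**6. Unequal withdrawal (illustration only).** Assume a placebo slope of 0.5 SD over the training period, a nicotine slope of 0.5 + 0.56 = 1.06, and stops split equally between weeks 2 and 5.5, with a plateau. The fitted slopes are 10.5/54.75 = 0.192 and 30.75/54.75 = 0.562, mean 0.377.
- 30% nicotine, 10% placebo: 1.06 × (0.7 + 0.3 × 0.377) − 0.5 × (0.9 + 0.1 × 0.377) = 0.862 − 0.469 = 0.39.
- 10% nicotine, 30% placebo: 1.06 × 0.938 − 0.5 × 0.813 = 0.994 − 0.407 = 0.59.

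The planned data would give 0.56 in both cases.

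**The case against.** **The trial is a proof of principle.** Its aim is whether nicotine present during training enhances training, and an effect under continued training is a legitimate target for that. This stands as an argument for naming that target. It does not rescue the intention-to-treat label.

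**Retention is better than the withdrawal section alone suggests.** Withdrawal by staff is discretionary. Study Procedures reschedules missed lozenges, outcome days and whole weeks, and allows up to 10 weeks for the follow-up visit. Poor attenders who are not withdrawn stay in and are tested. This stands: the gap comes only from people actually withdrawn.

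**Stronger readings that the documents do not support.**
- A reader might infer that the rule costs 20% of the data. The 25-to-20 allowance covers all non-completion, including refusal and loss to follow-up, and the staff-withdrawn share is not stated.
- A reader might assume that gains are lost after stopping. Scores of 0, 4, 0, 0 give −5/54.75 = −0.091, then 0.8 − 0.2 × 0.091 = 0.782, a 28% excess. The protocol's own background reports persistence at 6 months, so a plateau is the better-supported case.
- A reader might infer that excess stopping on nicotine would go unseen. Withdrawal counts remain observable, and the monitoring board reviews early withdrawals. No source supports a particular arm split, and people who cannot tolerate the lozenge are screened out before training.
- A reader might infer that withdrawn people drop out of the compliance comparison. It uses "the cumulative percentage of missed training sessions and lozenge administrations until each OCM time point", and nothing excludes their data up to withdrawal.

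**Conclusion.** The mismatch is real. The plan names an intention-to-treat analysis, but after withdrawal it provides no outcome data with which to carry one out. What it can estimate is the slope difference had everyone continued, assuming that those withdrawn would have followed the on-training slope of their arm.

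The size is uncertain and probably modest. Taking all of the 20% as withdrawals, equal by arm and with a plateau, the overstatement runs from about 5% to 25% depending on when people stop. The part that the protocol rule itself causes is smaller to the extent that some of the 20% refuse contact or are lost. With unequal withdrawal the direction is not fixed. The consequence for the measures taken only at weeks 0 and 10 needs none of these assumptions: anyone withdrawn before week 10 has no post-training value.

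One limit applies to the remedy too. Study Procedures randomizes before the lozenge exposure session and excludes some people before any outcome is measured. Post-withdrawal testing from week 0 onward narrows the gap to intention to treat but does not close it.

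**What to change.** In Withdrawal of Participants, item 3, separate stopping the lozenge or training from withdrawing consent for assessments. State that participants with a week-0 assessment who stop, or are withdrawn from, lozenge or training will be invited to the remaining scheduled outcome visits, at minimum week 10. The invitation holds if they are willing and the study physician has no safety objection, and it carries the usual outcome-day payment. State in Sample Size and Data Analysis that these scores enter the intention-to-treat model. Leave unchanged the decision on when lozenge or training stops, including for adverse effects.

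Reconcile the reference in Withdrawal item 1 to missed-day criteria in Study Procedures with that section, which contains none.

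**Cost.** Protocol and consent wording, plus a few extra visits for up to about 10 people (5 per group). Outcome visits are scheduled on non-drug days and Payment Detail already sets the payment. Some people will decline, and the estimated effect may be smaller. Outcomes not collected at the time cannot be recovered later.
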